Research Aims to be studied in this protocol:

Aim 2) Compare uptake of genetic testing for patient-directed standard of care vs. enhanced standard of care genetic services delivery models for 1,920 unaffected primary care patients. We will utilize a randomized trial design with clinic-level randomization to compare two standard of care models: a *patient-directed standard of care* model and an *enhanced* model. In the *patient-directed* model those identified by the clinical decision support (CDS) infrastructure as meeting testing criteria will be informed of their cancer risks, provided with educational resources, and offered the option to select genetic testing through a patient portal. This online portal will be overseen by HCI genetic counselors. The *enhanced standard of care* model in which primary care providers and patients are notified through CDS when criteria are met (the *enhancement* of standard of care) and of the availability of standard of care genetic services. We will compare uptake of genetic testing by model and by race/ethnicity and rurality.

Aim 3) Compare adherence to recommendations and other patient responses for the genetic services delivery models. We will compare the effects of the genetic services delivery models on adherence to management recommendations at 12 months after return of results, or last genetic services contact. We will assess cognitive (i.e., recall, comprehension, uncertainty, risk perceptions) and affective (i.e., test-related distress, positive reactions, decision regret) responses at 4 weeks, and communication (i.e., family, provider) interactions at 4 weeks and 12 months after last genetic services contact. We will also examine differences in effects by race/ethnicity and rurality.

7. Is this a multi-site study, where more than one site needs IRB approval?

Yes No

8. Background and Introduction:

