Need to address disparities in access and use of genetic services across population subgroups. Prior research has often shown that individuals from racial and ethnic minority groups have decreased access to and utilization of genetic services,¹⁰⁰ even when cost barriers are minimized.¹⁰¹ These disparities have been attributed to individual-level factors (e.g., awareness, knowledge, attitudes)¹⁰²⁻¹⁰⁴ and system-level factors (e.g., insurance, access to specialists, lower trust).^{103,105} One study with women diagnosed with breast cancer showed a strong desire for genetic testing among Latinas, but also that minority patients had more unmet needs for discussion of testing with providers.¹⁰⁶ Prior work has also indicated the importance of examining how race and ethnicity impact the delivery of genetic services. A randomized trial comparing in-person vs. telephone-based genetic counseling found that the effect of mode of delivery differed by race; minority women assigned to telephone counseling were the least likely to complete genetic testing.¹⁰⁷

Even less research has examined access and use of genetic services by rurality (rural/frontier vs. urban). Rurality is a critical issue for Utah; 96% of the landmass is defined as rural (<100 persons per square mile) and 70% as frontier (<7 persons per square mile).¹⁰⁸ Individuals in rural areas in the U.S. have less access to care¹⁰⁹ and worse health outcomes.^{110,111} Rural counties have higher incidence of cancers potentially preventable through screening.^{112,113} Some disparities in cancer mortality are likely due to barriers to accessing health services in rural areas.¹¹³ Clinical sites in rural areas may not have physicians knowledgeable about genetics.¹¹⁴ In addition, in rural/frontier regions, clinics and hospitals can be hundreds of miles from patients' homes, so rural/frontier residents have less access to specialty genetics care.^{70,115}

Citations can be found in the appropriate Documents & Attachments section.

IRB_00123563

Created: 6/5/2019 3:01 PM

IRB_00123563

2. Study Location and Sponsors

PI: [name]

Submitted: 3/5/2019

Title: Broadening the Reach, Impact, and Delivery of Genetic Services**2. Study Location and Sponsors**

1. Add all locations applying for approval of research via the University of Utah IRB or Human Research Protection Program (HRPP).

Click the appropriate button(s) below to add locations:

Site Name	Investigators Name	Covered Entity	Sub Sites

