Aim 2 analyses will address the dimensions of Reach, Effectiveness, Adoption, and Implementation from our conceptual framework. For Effectiveness, we will be testing for equivalence between study arms in uptake of genetic testing. We will check randomization by comparing demographic characteristics between patients in the two arms. Any characteristic(s) that are significantly different will be controlled for in the multivariable analysis. We will examine descriptive statistics, and will use Fisher's Exact test with a two-sided 0.05 significance level for univariate comparison of proportions to examine the association between study arm and uptake of genetic testing. We will next build multilevel multivariable logistic regression models to examine the effect of study arm on the outcome controlling for clinic-level (clinic type, patient volume, patient composition, number of providers), provider-level (specialty, years in practice, gender), and patient-level (e.g., sociodemographic, clinical) variables. We will examine the intra-class correlation (ICC) by clinic and provider. If a significant ICC is observed, the regression models will be extended to include random effects for clinic or provider, and fit using software for generalized mixed models. Covariates will be included in models if significant in unadjusted analyses. For Reach, using the multivariable regression models with interaction terms, we will examine whether the effects of study arm on uptake of genetic testing is modified by race/ethnicity or rurality. For Adoption, we will examine the proportions of providers and patients who access educational resources and with referrals, and whether this differs by population subgroup. For Implementation, we will assess responses to patient portal messages and completion of study workflows. Statistical significance will be assessed as $p < 0.05$; SAS 9.4 and/or Stata 15.1 will be used for analysis.

Aim 2 Sample Size

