Progress for this study remains ongoing although delayed by the technical implementation timeline. Enrollment at the Utah site is expected to commence in April with NYU enrollment projected to begin in June.

The study team has completed building questionnaires in RedCap and is prepared to begin enrollment once patients have completed the necessary clinical procedures.

- What results (preliminary or final) have been obtained from the study? If the study is part of a multi-center trial, this should be stated and any available results provided. If there are no results that are appropriate to report to the IRB at this time, this should be stated and explained:**

Because this study has not enrolled any participants, there are no results to disclose at this point.

Please attach any abstracts or publications:

Name Version Date Created Date Modified Date Approved

There are no items to display

- Describe participant enrollment and its effect on the study design and scientific merit. If under-accrued, describe any plans for increasing enrollment during the next approval period. If a multicenter trial, also discuss enrollment at other sites.**

This study has no participants enrolled. Enrollment is expected to begin at Utah in April and at NYU in June.

IRB_00115509 - CR_3/9/2020 2:18 PM**Created: 3/9/2020 2:18 PM****PI:** [name]**Submitted: 3/23/2020****Title:** Broadening the Reach, Impact, and Delivery of Genetic Services**HELP?**

— Progress of Sites and Enrollment —

Select each site to update the enrollment information.**List of Study Controlled Locations**

	Site Name	Investigator's Name	Enrollments since Last CR	Enrollments as of Today	Non English Speakers	Withdrawn
View	NYU School of Medicine	[name]		0	0	0
View	University of Utah	[name]		0	0	0

IRB_00115509 - CR_3/9/2020 2:18 PM**Created: 3/9/2020 2:18 PM****PI:** [name]**Submitted: 3/23/2020****Title:** Broadening the Reach, Impact, and Delivery of Genetic Services**HELP?**

— 3. Problems & Events —

Provide narrative summary of any available information regarding adverse events which

- 1. have occurred since the last IRB review.**

- There have been no adverse events.

Have any additional risks to participation in this study been identified (from any site or**other relevant source) since last approval? If reports or amendments identifying additional**

- 2. risks have been submitted since last approval, please mark ◊yes◊.**

- Yes No

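### The pooled arm-by-rurality test has no arm-by-health-system term, so if rural patients are mainly in Utah it can absorb a between-system difference in arm effect

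*Combined protocol and SAP*

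**What the plan says.** Aim 2 in the Study Introduction (section 1, item 6) sets the objective: "We will compare uptake of genetic testing by model and by race/ethnicity and rurality". Aim 3 adds: "We will also examine differences in effects by race/ethnicity and rurality". In section 4 (Study Information), item 9, the Aim 2 Analysis tests this for Reach with interaction terms: "we will examine whether the effects of study arm on uptake of genetic testing is modified by race/ethnicity or rurality". The Aim 3 Analysis, which is placed under Effectiveness, says effect modification will be examined as in Aim 2.

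The same item describes the model. It is multilevel logistic regression, "controlling for clinic-level (clinic type, patient volume, patient composition, number of providers"), followed by provider-level variables and an open list of patient-level variables. Two rules govern its form: "Covariates will be included in models if significant in unadjusted analyses", and "If a significant ICC is observed, the regression models will be extended to include random effects for clinic or provider". Health system is not named as a covariate, no arm-by-system term is mentioned, and no system-specific analysis is described. Nor is stratification of the clinic randomization by system.

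The case for studying rurality, in item 8 of the Introduction, rests on one state: "Rurality is a critical issue for Utah; 96% of the landmass is defined as rural". That is a share of land, not of patients. The rural share among patients is not given for Utah or for NYU. The site pages of the last two continuing reviews give 960 approved enrollments per system.

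**The concern.** If the rural group comes largely from one system while the urban group mixes both, the pooled arm-by-rurality coefficient compares two things at once: rural with urban, and Utah with a Utah-NYU mixture. Any difference in arm effect between the systems then enters the rurality coefficient.

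The planned safeguards do not deal with this. The covariate rule concerns main effects, and a health-system main effect adjusts the level of uptake, not the difference between arms. A clinic random intercept enters only if the ICC is significant. Where rural patients attend rural clinics it leaves the problem as it is. Where clinics mix rural and urban patients it may shrink the bias, but it does not remove it.

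At stake is a named objective of both aims. The trial could report that the patient-directed model works better or worse for rural patients when the two systems merely differ, or it could mask a real rural difference.

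**Working it through.** **The plan's own interaction figure.** The plan gives 1,710 observations for 80% power at two-sided 0.05 to detect an interaction odds ratio of 1.5. With 0/1 coding, the smallest possible variance of the interaction log OR is 64/N (four equal cells, uptake 0.5). The minimum N is therefore 64 × (1.960 + 0.842)² / (ln 1.5)² ≈ 3,056, so 1,710 is not reproduced. That is a separate matter and is not used below.

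**Inputs.** From the documents: two systems, 960 patients each, a logistic model with an arm-by-rurality term, and no system term. Assumed, because the documents are silent: equal arms within each system (480 per arm); Utah rural share r of 10-30%; no rural NYU patients; uptake of 20-30% in the enhanced arm; no true rurality effect; an arm odds ratio of 1.5 in Utah and 1.0 at NYU. The reverse direction would push the apparent odds ratio below 1. The fits ignore clustering and include no clinic effects.

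**Share absorbed.** NYU's share of the urban group is 960 / [960 + 960(1 − r)] = 1/(2 − r), which is 0.526, 0.556 and 0.588 for r = 0.1, 0.2 and 0.3. The rural arm effect is Utah's. The urban arm effect is roughly the share-weighted average of the two systems. The difference is therefore about 53-59% of the arm-by-system log OR.

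**Worked case on the logistic scale (r = 0.1, 20% uptake in both systems).** Utah patient-directed odds are 0.25 × 1.5 = 0.375, so uptake is 0.2727. Urban patient-directed uptake is (480 × 0.20 + 432 × 0.2727)/912 = 0.2345, with odds 0.3063. The urban arm OR is 0.3063/0.25 = 1.225. The apparent rurality OR is 1.5/1.225 = 1.224; the true value is 1.0.

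| Utah rural share | 20% both | 30% both | 20% Utah, 30% NYU | False-positive rate (nominal 5%) |
|---|---|---|---|---|
| 10% | 1.224 | 1.230 | 1.259 | about 7-8% |
| 20% | 1.239 | 1.245 | 1.274 | 9-10% |
| 30% | 1.256 | 1.261 | 1.290 | 12-14% |

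The same arithmetic with 30% uptake in Utah and 20% at NYU gives slightly less, 1.20-1.23.

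**Variations on the three tabulated uptake patterns.**
- Adding a health-system main effect leaves 1.22-1.29.
- Adding arm-by-system returns 1.00 and a 5% error rate.
- If 2% of NYU patients are rural, the apparent OR is 1.15-1.25.
- An arm-by-system OR of 2.0 gives 1.40-1.53 and false-positive rates of 11-31%.
- If the arm effect is equal in both systems, there is no bias.

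**Cost in precision (25% uptake, p(1 − p) = 0.1875, no arm effect).** With arm-by-system in the model, the urban comparison is Utah only.
- r = 0.1: pooled SE = √[2/(48 × 0.1875) + 2/(912 × 0.1875)] = 0.484; with the term, √[2/(48 × 0.1875) + 2/(432 × 0.1875)] = 0.497.
- r = 0.3: pooled SE = √[2/(144 × 0.1875) + 2/(816 × 0.1875)] = 0.295; with the term, √[2/(144 × 0.1875) + 2/(336 × 0.1875)] = 0.325.

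**Aim 3 questionnaires.** The continuing review created in December 2023 counts 237 questionnaire completers at Utah and 98 at NYU. With the same assumed rural shares, NYU would be 98/(98 + 237 × 0.9) = 31% to 98/(98 + 237 × 0.7) = 37% of the urban group, so the share absorbed is smaller there.

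**The case against.** The strongest reply is that both conditions for bias are assumed. A reader might infer from the Utah background that rural patients come essentially from Utah. The documents give only a landmass figure, and their silence on rural NYU patients does not show that there are none. A reader might also infer a differing arm effect from the separate timelines, such as "Enrollment at the Utah site is expected to commence in April with NYU enrollment projected to begin in June", and from NYU's later delays. Those passages concern timing. Nothing in them says that the difference between arms changed, and the arms are described once for both systems. Both limits stand, and the finding has to be conditional.

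Three further replies have some weight. Item 9 asks for a summary, and its patient-level covariate list is open, so a system term is not excluded. But none is specified, and an ordinary covariate would not help. Secondly, rurality is not randomized, and a pooled contrast fairly describes how the arm effect differs between rural and urban enrollees. That holds for description, but a reader will take the result as being about rurality. Thirdly, the fix does not solve power: within Utah (N = 960, no clustering), power for an interaction OR of 1.5 is about 9-15% at 10% rural and 15-30% at 30% rural, for uptake of 10-50%. That is true, but it is a separate weakness, and the pooled model does little better (9-16% and 17-35%).

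**Conclusion.** The point holds as a conditional one. The plan tests arm-by-rurality over two systems without an arm-by-system term, and that leaves the result open to confounding. With no rural NYU patients and 10-30% rural in Utah, about 53-59% of any arm-by-system log OR passes into the rurality term. An arm-by-system OR of 1.5 would show as about 1.22-1.29. The rural shares, uptake and arm-by-system ORs are assumptions.

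Stronger readings are not supported. A reader might conclude that the rurality question cannot be answered. It can be, because the effect is identifiable within Utah as long as rural and urban patients are both enrolled there. A reader might extend the point to race/ethnicity, but the documents give no racial or ethnic mix by system on which to base that. A reader might speak of a Reach analysis in both aims, but only Aim 2 has one; Aim 3 falls under Effectiveness. This is an inexpensive improvement to a named secondary question. It does not bear on the equivalence comparison of the two arms.

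**What to change.** In the Aim 2 Reach model and the Aim 3 effect-modification models, state that health system and arm-by-health-system are included whenever arm-by-rurality is tested, whatever their significance. Alternatively, estimate arm-by-rurality within Utah. Report the number of rural and urban patients by system and arm. If rural patients prove to be nearly all from Utah, word the rurality conclusion as applying to Utah.

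The cost is about a sentence in the analysis text and a slightly wider interval, because NYU patients no longer serve as the urban comparison for Utah's rural patients. In the 25%-uptake example the standard error rises by about 3% at 10% rural (0.497/0.484) and about 10% at 30% rural (0.325/0.295), before clustering. No extra data are needed beyond rurality and health system for each patient.

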PROTOCOL TITLE: Broadening the Reach, Impact, and Delivery of Genetic Services (BRIDGE)

NCT NUMBER: NCT03985852

PROTOCOL DATE: 06/05/2019

The full trial protocol is available at:

[name], [name], [name], et al. Comparing models of delivery for cancer genetic services among patients receiving primary care who meet criteria for genetic evaluation in two healthcare systems: BRIDGE randomized controlled trial. *BMC Health Sciences Research*. 2021;21:542. doi:10.1186/s12913-021-06489-y

Date: Tuesday, August 6, 2024 10:49:19 AM

[Print](#)[Close](#)**IRB_00123563****Created:** 6/5/2019 3:01 PM**PI:** [name]**Submitted:** 3/5/2019**Title:** Broadening the Reach, Impact, and Delivery of Genetic Services**IRB_00123563**

1. Contacts and Title

1. Study Introduction

1. Responsible Investigator:

[name]

Email	Training	Col Date
[contact]	4/25/2022 SMCG	3/19/2024

a. Position of the Investigator:

Faculty or Non-Academic Equivalent

Student

Staff

Resident/Fellow

Other

2. Contact Persons for the Responsible Investigator:

Name	Email	Training
[name]	[contact]	2/22/2023 MCG
[name]	[contact]	3/4/2024 SMCG
[name]	[contact]	3/21/2022 SMCG
[name]	[contact]	1/9/2023 SMCG

3. Guests of the Responsible Investigator:

Last Name	First Name	E-Mail
[name]	[contact]
[name]	[contact]
[name]	[contact]
[name]	[contact]
[name]	[contact]

4. What type of application is being submitted?

New Study Application (or Amendment/Continuing Review)

5. Title Of Study:

Broadening the Reach, Impact, and Delivery of Genetic Services

6. Study Purposes and Objectives:

The proposed study will employ an implementation science framework to compare two models of genetic services delivery for 1,920 patients in a randomized controlled trial with clinic-level randomization. We hypothesize that uptake of genetic testing (Study Aim 2) and adherence to management recommendations (Study Aim 3) will be equivalent between the genetic services delivery models. We propose the following Specific Aims:

Aim 1) Identify primary care patients who qualify for genetic risk assessment in two healthcare systems using a CDS infrastructure to automatically evaluate family history.

*This aim has already been studied in IRB #105797. We will be utilizing this tool that is now available. Aim 1 will not be analyzed in this protocol but is part of our overall research model.

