Sample size for Aim 2 was calculated using PASS 15 based on an equivalence test for the difference of two proportions in a cluster-randomized design. Sample sizes of 480 in the patient-directed arm and 480 in enhanced standard of care arm, which were obtained by sampling 32 clusters (clinics) with 15 participants each and 16 clusters (clinics) with 30 participants each, respectively, achieve 80% power to detect equivalence. The margin of equivalence, given in terms of the difference between proportions, extends from -0.10 to 0.10. The calculations assume Likelihood Score Tests (Farrington & Manning) were used with an ICC of 0.05, and a significance level of 0.05. We believe that this is likely an overestimate of ICC based on our prior work. This sample size is sufficient for a multilevel multivariable regression analysis and achieves >95% power to detect a small effect size (0.02) attributable to 1 independent variable using an F-Test with an alpha of 0.05, adjusted for an additional 20 independent variables. To examine effect modification, sample size is calculated based on logistic regression of a binary response variable (Y) on a binary independent variable (X) and a binary confounder variable (Z). A sample size of 1,710 observations achieves 80% power at a 0.05 significance level to detect the X-Z interaction odds ratio of 1.5, using a two-sided Wald test. We will therefore enroll 1,920 patients in the Aim 2 trial to allow for about 10% attrition.

Aim 3 Analysis

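### The regression power above 95% claimed at 960 patients does not hold for study arm, which is randomised by clinic: at the plan's ICC of 0.05 it is about 85%

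*Combined protocol and SAP*

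**What the plan says.** All the figures are in item 9 of section 4, Study Information.

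- **Equivalence test (Aim 2 Sample Size).** The plan takes 480 patients per arm, obtained by "sampling 32 clusters (clinics) with 15 participants each and 16 clusters (clinics) with 30 participants each". That makes 960 patients in 48 clinics. The tests "were used with an ICC of 0.05, and a significance level of 0.05", and the plan adds: "We believe that this is likely an overestimate of ICC based on our prior work".
- **Regression (same paragraph).** "This sample size is sufficient for a multilevel multivariable regression analysis", and it "achieves >95% power to detect a small effect size (0.02) attributable to 1 independent variable using an F-Test with an alpha of 0.05", with 20 further covariates. No ICC, design effect or clinic-level degrees of freedom accompany this statement, and the single variable is not named.
- **Use of the regression (Aim 2 Analysis).** The plan will "build multilevel multivariable logistic regression models to examine the effect of study arm on the outcome".
- **Level of assignment (section 1, Study Purposes and Objectives).** The models of care are compared "in a randomized controlled trial with clinic-level randomization".
- **Final enrolment (end of the Aim 2 Sample Size paragraph).** "We will therefore enroll 1,920 patients in the Aim 2 trial to allow for about 10% attrition". No clinic count is given for 1,920.

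**The concern.** The paragraph allows for clustering in the equivalence test and then, for the same 960 patients, gives a regression power that matches a calculation on independent patients. A covariate that varies within clinics loses little or no power to clustering. Study arm is constant within a clinic, so it loses the most, and it is the one effect that the Aim 2 Analysis section says this model is built to examine. Because the sentence calls the regression multilevel, a reader will assume that clustering is already in the figure and will apply it to arm.

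At stake is how a non-significant arm coefficient would be read. Power above 95% implies a chance below 5% of missing the stated effect. If the true chance is nearer 15%, such a result is weaker evidence than the plan suggests. That matters in a trial whose hypothesis is that the two models of care are equivalent.

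**Working it through.** **Inputs from the plan:** f² = 0.02; one tested variable; 20 covariates; two-sided alpha 0.05; 480 patients per arm; 32 clinics of 15 and 16 clinics of 30; ICC 0.05.

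**1. Reproduce the stated figure.** Treat the patients as independent. The noncentrality is λ = f²·N = 0.02 × 960 = 19.2, with 1 and 960 − 22 = 938 degrees of freedom. Power is **99.2%**, consistent with the plan's statement.

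**2. Apply the design effect to study arm.** For clinic size m, the design effect is 1 + (m − 1) × ICC.

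- Clinics of 15: 1 + 14 × 0.05 = 1.70, so the effective n is 480/1.70 = 282.4.
- Clinics of 30: 1 + 29 × 0.05 = 2.45, so the effective n is 480/2.45 = 195.9.
- Balanced-equivalent total: 4 × 282.4 × 195.9 / (282.4 + 195.9) = 462.7.
- λ = 0.02 × 462.7 = 9.25.

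Power is **84.6%** with clinic-level degrees of freedom (48 − 2 = 46) and **85.9%** with degrees of freedom from the effective N (462.7 − 22, about 441). If the four clinic-level covariates in the Aim 2 Analysis section each cost one degree of freedom (an assumption, giving 42), it is 84.4%.

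**3. Repeat at the planned enrolment.** The plan gives no clinic count at 1,920, so both possibilities are shown, at ICC 0.05. The 1,728 row is 1,920 less 10%.

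| Patients | Clinics | Effective N | Power, clinic df | Power, df from effective N |
|---|---|---|---|---|
| 960 | 48 | 462.7 | 84.6% | 85.9% |
| 1,728 | 48 | 580.8 | 91.6% | 92.5% |
| 1,920 | 48 | 600.0 | 92.4% | 93.3% |
| 1,920 | 96 | 925.3 | 98.9% | 99.0% |

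**4. Vary the ICC.** Power for study arm in 48 clinics, lower value with 46 df and upper with df from the effective N:

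| ICC | 960 patients | 1,920 patients |
|---|---|---|
| 0.02 | 94.8 to 95.5% | 99.3 to 99.5% |
| 0.03 | 91.7 to 92.7% | 97.8 to 98.2% |
| 0.04 | 88.2 to 89.4% | 95.5 to 96.1% |
| 0.05 | 84.6 to 85.9% | 92.4 to 93.3% |

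Power reaches 95% for arm at an ICC of about 0.019 to 0.022 with 960 patients, and about 0.042 to 0.044 with 1,920 in 48 clinics.

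**5. Check against a binary outcome.** The planned model is logistic, while the F-test is linear. Beta-binomial clinics were simulated at overall uptake of 20%, 30% and 50% (assumed, since the power calculation states no uptake). The arm difference was 2·√0.02·√(p(1 − p)), that is 11.3, 13.0 and 14.1 percentage points. Each setting was analysed by a weighted t-test on clinic means with 46 df. At ICC 0.05, power was 84.2 to 86.4% at 960 and 92.3 to 93.5% at 1,920 in 48 clinics. The linear approximation is adequate here.

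**The case against.** There is a reasonable case that this is only a point of wording.

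- **The sentence names no variable.** It refers to one independent variable, and for a patient-level covariate the figure is right. This stands, and it is why the fault is one of unstated scope rather than a miscalculated F-test. But arm is the only effect that the Aim 2 Analysis section names as the purpose of the model.
- **Arm already has a clustered power calculation.** Effectiveness is defined as equivalence, and that test is powered at 80% with the ICC included. This stands too: the equivalence power is untouched. At the assumed uptakes, f² = 0.02 corresponds to 11.3 to 14.1 points, outside the 0.10 margin, so the regression figure concerns detecting a difference and not the equivalence claim itself.
- **The trial enrols 1,920, not 960.** At 1,920 the shortfall is about 2 to 3 points, and only if clinics stay at 48. This limits the practical size of the problem. But the power statement is made for 960, and the plan does not say that clinics will double.
- **ICC 0.05 may be too high.** The plan says so, and covariate adjustment may lower the residual ICC. At 1,920 in 48 clinics, an ICC of 0.04 is enough to restore 95%. At 960 the ICC must fall to about 0.02, and the plan offers no value other than 0.05.
- **The inputs do not support great precision.** The effect-size scale, the degrees of freedom and the adjusted ICC are all unstated. The results are best read as about 85% and about 92 to 93%. No choice of degrees of freedom brings either to 95% at ICC 0.05.

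**Conclusion.** The concern holds. As written, the power above 95% is not delivered for study arm at the ICC and clinic sizes in the same paragraph. At 960 patients it is about 85%, so the chance of missing the stated effect is about 15% rather than below 5%. At 1,920 in the same 48 clinics the chance is about 7 to 8%, and with 96 clinics about 1%.

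The conclusion rests on three things: reading the figure as applying to study arm, taking ICC 0.05 for the regression because it is the only value given, and using the plan's linear F-test as an approximation to the logistic model. No study-arm figure in the working falls below 80%, and the sample size does not depend on this sentence: 960 comes from the equivalence test, and 1,920 from the interaction requirement of 1,710 plus attrition. What must change is the stated figure, not the design.

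**What to change.** Rewrite the one sentence in the Aim 2 Sample Size section in either of two ways.

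1. Restate the power for study arm with the design effect, ICC, clinic count and degrees of freedom. For example: at ICC 0.05 with clinic-level degrees of freedom, power for study arm at f² = 0.02 is about 85% with 960 patients, and about 92% with 1,920 patients in 48 clinics. If more clinics are planned at 1,920, give the number and the matching power.
2. Keep the figure above 95% but limit it explicitly to patient-level covariates, or to study arm at an ICC of about 0.02 or lower, and give the prior-work estimate that supports such an ICC.

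The cost is one sentence and a less favourable figure. No extra patients are needed and the analysis does not change.
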